# 8 Study Populations

Subjects will all be male, at least 18 years of age, and will have prostate cancer that is locally confined or extracapsular with no posterior extension (i.e., not involving the rectum) with a planned treatment regime of radiotherapy by means of IMRT.

# **9** Analysis Populations

The analysis populations are defined in compliance with E9 guidance from the ICH: Statistical principles for clinical trials.

#### Intent-to-Treat (ITT) Population

Intent-to-Treat (ITT) population will include all randomized subjects, regardless of whether they underwent a surgery or not. All subjects in the ITT population will be analyzed as members of the group to which they were assigned irrespective of actual treatment received.

The ITT population will be used for a sensitivity analysis for the study co-primary endpoints.

#### Per-Protocol (PP) Population

The Per-protocol (PP) population is a subset of the ITT population, and will include:

- All subjects randomized to the Control group.
- *ProSpace* group subjects who were marked and implanted as planned.

The PP population will be used for analyses of the study's primary and secondary endpoints (efficacy and safety).

A listing of all protocol deviations will be evaluated prior to the database lock by the study's medical monitor (clinical expert).

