2.2.3.2 Exclusion Criteria

Prospective subjects must **not** meet *any* of the exclusion criteria to participate in this clinical study. These include:

- Pelvic lymph node radiotherapy is planned;
- Any prior invasive malignancy (except non-melanomatous skin cancer) unless the subject has been disease free for a minimum of 5 years;
- Prior radical prostatectomy;
- Prior cryosurgery or radiotherapy for prostate cancer, or other local therapy for prostate cancer;
- Prior radiotherapy to the pelvis, including brachytherapy;
- American Urological Assn. (AUA) Symptom Score ≥ 20 ;
- Active inflammatory bowel disease;
- Known or suspected rectal carcinoma;
- History of prior surgery involving the rectum or anus;
- Venereal warts in the region;
- Prior surgical procedure involving the peri-rectal and/or peri-prostatic area;
- Current urinary tract infection;

- Acute or chronic prostatitis;
- Acute infection requiring intravenous antibiotics at the time of screening;
- Uncontrolled bleeding disorders;
- Unsuitability for anesthesia in the opinion of the anesthesiologist;
- Currently taking anticoagulants or NSAIDS that cannot be stopped for sufficient time prior to the implantation procedure;
- EU citizens may not be enrolled by sites located at any site that is not GDPR compliant;
- Currently incarcerated or
- Participation in any other investigational drug, biologic or medical device study within the 30 days prior to the study surgery.

Intra-operative exclusion criteria for the balloon arm subjects only:

• Inability to perform proper dissection between prostate and rectum.

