2.2.5 STUDY DESIGN

2.2.5.1 OVERALL STUDY DESIGN

This study will be a prospective, multi-center, randomized, double-arm, single blind, concurrently controlled study to assess the safety and efficacy of the BioProtect Balloon Implant System in prostate cancer subjects undergoing radiotherapy by means of IMRT.

Subjects will be randomized in a 2:1 ratio (balloon implantation:control) to receive either IMRT +marking + balloon implantation or IMRT +marking. The balloon will be inserted during the same session of the marking.

Subjects will be blinded to study assignments. It is not practical to blind the surgeon or surgeon's staff since they will participate in the insertion procedure and/or be responsible for

maintaining source documentation. Additionally, the core lab cannot be blinded since the balloon will be visible on the CT images.

All subjects enrolled in the study will be included in an "intent-to-treat" analysis regardless of failure to complete the required follow-up examinations. Subjects will be considered enrolled in the study for the purposes of an intent-to-treat analysis only after they have provided Informed Consent and have been randomized. Preliminary data will be captured for subjects excluded intraoperatively, documenting the reason(s) for exclusion. It is anticipated that very few, if any, subjects will be excluded intraoperatively. Sites will maintain a log of screening failures, documenting the reason for failure. Additionally, subjects who are randomized but not implanted (e.g., due to an adverse event that prevents or significantly delays their radiation treatment) may be removed from the study. Such removals will be documented and reported appropriately. Subjects who are screening failures or who are removed from the study prior to implantation will be excluded from analysis.

This study will utilize a core laboratory for analysis of CT images. Post implantation CT images for the *Balloon Group* will be compared to pre-implantation images to demonstrate the change in distance and potential for rectal protection provided by the balloon.

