2.3.2 ANALYSIS POPULATIONS

The intent-to-treat (ITT) population consists of all subjects randomized for the study. The primary analysis population will be based on a Per-Protocol population consisting of ITT in the Control Group and subjects who were randomized to the balloon Group. The ITT population analysis will be included in a sensitivity analysis.

The primary analyses will be completed using a Per-Protocol (PP) Population consisting of subjects who were randomized to and received the balloon device or were randomized to the *Control Group*. It is anticipated that there may be one or two subjects that get randomized to the balloon device, but are not implanted. These subjects will not be included in the PP population or be required to be followed per the protocol. However, the subjects will be included as failures in a sensitivity analysis in the primary analyses for the study.

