2.4 DEVICE DESCRIPTION

The balloon is a biodegradable balloon system indicated to temporarily position the anterior

rectal wall away from the prostate thereby reducing the radiation dose delivered to the anterior rectum in patients undergoing IMRT for the treatment of prostate cancer. The balloon e is made of Poly (Llactide-co-ɛ-caprolactone), commercial name RESOMER[®] LC 703 S, manufactured by Evonik Industries AG, GmbH.

The system is comprised of: an echogenic needle,

which is inserted while injecting saline slowly to facilitate the dissection of the plane between the prostate and rectum; a single use, biodegradable, pre-folded, inflatable balloon; and an internal stainless steel inflation tube which is attached to the balloon (balloon deployer) within a stainless steel retaining tube with a PTFE outer sheath. The balloon is folded inside the outer sheath and a balloon plug is attached to the tip of the

internal inflation tube. The tube allows for the insertion and inflation of the balloon, and sealing of the balloon by the plug attached to its tip. The balloon is inflated slowly with saline (16-17 ml), sealed, and the deployer is then removed, leaving the inflated balloon in situ. The balloon deployer is for single use only.

The BioProtect Balloon Implant Systemis supplied

sterile and for one time use. The balloon is implanted transperineally using TRUS guidance.

Once inserted, the inflated balloon gradually hydrolyzes and is fully degraded at 12 months post implantation based on low absorption CT. The products of biodegradation are absorbed and cleared via respiration and renal filtration.

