#### 10.3.6 Safety

#### 10.3.6.1 Adverse Events

An adverse event (AE) is as any clinically significant unfavorable and unintended medical occurrence, including any abnormal sign (e.g., physical exam), symptom, or disease, whether or not it is considered related to the device being studied in a subject.

Adverse event severity will be graded from 1-5, according to the Common Terminology Criteria for Adverse Events (CTCAE) (Version 4.0) as provided by the US Department of Health and Human Services, NIH, and the National Cancer Institute.

Adverse Events will be categorized with respect to relationship to the device as "not related", "possibly related", "probably related", or "definitely related", as well as by degree of severity.

Statistical Analysis Dlan	Client/Project	BioProtect BP-007
Statistical Analysis Flan	Version and Date	V2 05-DEC-2021

AEs will be characterized by CEC adjudication, when available, for marking/implantation procedurerelatedness, device-relatedness, IMRT-relatedness, rectum-relatedness, and seriousness. Marking/implantation procedure relatedness adjudication will be further subdivided into relatedness to ProSpace implantation, marker implantation, administration of anesthesia, and use of foley catheter. If there are AEs for which the CEC determination for procedure relatedness or seriousness differs from the determination of the study site, the site-reported AE determinations will be listed separately.

Any AEs reported prior to the marking/implantation procedure will be listed as medical history. AEs that begin during or after the marking/implantation procedure will be counted and listed as AEs. If an AE is specified as starting before the marking/implantation procedure, any event with an increase in severity reported during or after the procedure will be counted and listed as an AE. All AEs will be summarized by treatment group.

Unless otherwise specified, summary counts of AEs will be the number of subjects reporting AEs and not the number of events reported. If the same AE is reported multiple times for the same subject, it will only appear once for that specified treatment and category in the summary tables.

The following AE summaries will be provided:

- Overall Summary of AEs, which will summarize all events, all device-related events, all procedure-related events, all serious events, all device-related serious events, and all procedure-related serious events
- All AEs by Type

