#### Tables

Table 14.2.9.2, Analysis of EPIC Sexual Domain Scores at IMRT Midpoint and Final IMRT Visit, Per-Protocol
Population
Table 14.3.1.1, Overall Summary of Adverse Events, Per-Protocol Population
Table 14.3.1.2.1, Adverse Events by Term, Per-Protocol Population
Table 14.3.1.2.2, Adverse Events by Term and Timing, Per-Protocol Population
Table 14.3.1.3.1, Device-Related Adverse Events Term, Per-Protocol Population
Table 14.3.1.3.1, Device-Related Adverse Events Term and Timing, Per-Protocol Population
Table 14.3.1.4.1, Procedure-Related Adverse Events by Term, Per-Protocol Population
Table 14.3.1.4.2, Procedure-Related Adverse Events by Term and Timing, Per-Protocol Population
Table 14.3.1.5.1, Adverse Events Rated as Serious by Term, Per-Protocol Population
Table 14.3.1.5.2, Adverse Events Rated as Serious by Term and Timing, Per-Protocol Population
Table 14.3.1.6.1, Device-Related Adverse Events Rated as Serious by Term, Per-Protocol Population
Table 14.3.1.6.2, Device-Related Adverse Events Rated as Serious by Term and Timing, Per-Protocol Population
Table 14.3.1.7.1, Procedure-Related Adverse Events Rated as Serious by Term, Per-Protocol Population
Table 14.3.1.7.2, Procedure-Related Adverse Events Rated as Serious by Term and Timing, Per-Protocol
Population
Table 14.3.2.1, AEs by CTCAE Grade, Per-Protocol Population
Table 14.3.2.2, Device-Related Severe Adverse Events by Term, Per-Protocol Population
Table 14.3.2.3, Procedure-Related Severe Adverse Events by Term, Per-Protocol Population
Table 14.3.3.1, Listing of Adverse Events Leading to Study Discontinuation, Per-Protocol Population
Table 14.3.3.2, Listing of Adverse Events Leading to Death, Per-Protocol Population
Table 14.3.4.1, Perineal Healing Status Each Week During Radiation Therapy, Per-Protocol Population
Table 14.3.4.2, Perineal Healing Status at Final Radiation Therapy Visit, Per-Protocol Population

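### All 18 general adverse-event tables are titled Per-Protocol, so an abandoned balloon implantation falls outside them and need not be followed; the primary safety decision is little affected

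*SAP*

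**What the plan says.** SAP section 9 defines two populations, ITT and Per-Protocol (PP). PP contains all randomised Controls and, on the balloon side, only ProSpace "group subjects who were marked and implanted as planned". The same section assigns PP to the primary and secondary endpoints. It does not mention general AE summaries.

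SAP 10.3.6.1 states "All AEs will be summarized by treatment group" and names no population. The restriction appears in the section 12 table list, where the general AE tables run from "Table 14.3.1.1, Overall Summary of Adverse Events, Per-Protocol Population" to "Table 14.3.3.2, Listing of Adverse Events Leading to Death, Per-Protocol Population".

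On the subjects concerned:

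- Protocol 2.2.3.2 has a criterion headed "Intra-operative exclusion criteria for the balloon arm subjects only", namely failure to achieve proper dissection between prostate and rectum.
- Protocol 2.4 describes the system's needle, "which is inserted while injecting saline slowly to facilitate the dissection of the plane between the prostate and rectum".
- Protocol 2.3.2 says of balloon subjects who are not implanted: "These subjects will not be included in the PP population or be required to be followed per the protocol".
- Protocol 2.2.5.1 gives the expected number: "It is anticipated that very few, if any, subjects will be excluded intraoperatively".

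**The concern.** A subject whose dissection is begun and then given up has been exposed to the needle and the saline injection. The protocol's benefit-risk discussion names rectal perforation and injury during implantation as the main risk of the device. His data belong in any summary of procedural harm, but he is outside PP. The loss runs one way, because no Control can leave PP by this route.

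Two things are at stake. The first is the aggregate AE record: serious, procedure-related and device-related tables would carry neither his event nor his place in the denominator. The second is data collection. Protocol 2.2.6.5 records AEs through discharge, but the primary safety definition needs an event lasting at least 2 days. If follow-up is not required, the duration of an injury seen that day, and anything with later onset, may never be recorded. No choice of analysis population can restore data that were not collected.

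**Working it through.** 1. **Table count (SAP section 12).** 14.3.1.1 gives 1. The pairs under 14.3.1.2 to 14.3.1.7 give 6 × 2 = 12 (number 14.3.1.3.1 is used twice). 14.3.2.1 to 14.3.2.3 give 3, and 14.3.3.1 and 14.3.3.2 give 2. The total is 1 + 12 + 3 + 2 = 18, all titled Per-Protocol. The two perineal-healing tables are not counted. Demographics, medical history and procedure information each have a PP and an ITT version; these 18 do not.

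2. **Expected number.** Protocol 2.2.5.1 allows for none excluded intraoperatively. Protocol 2.3.2 foresees one or two not implanted for any reason. The range for abandoned attempts is therefore zero to two.

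3. **Planned safety power reproduced.** Inputs from Protocol 2.3.4.4: 136 balloon and 68 Control subjects, rates 19% and 21%, margin 0.15, one-sided 0.025, Farrington-Manning. Power = Φ[(0.15 − (0.19 − 0.21) − 1.96·SE0)/SE1], where SE0 uses the rates constrained to a 0.15 difference and SE1 the assumed rates. With SE0 = 0.0550 and SE1 = 0.0598 this is Φ(1.04) = 85.1%. Exact binomial enumeration gives 86.0%. The plan states 85%.

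4. **Effect on the primary test.** The planned rates give 0.19 × 136 ≈ 26 and 0.21 × 68 ≈ 14 events. The statistic is z = (p_b − p_c − 0.15)/SE0. For 26/136 against 14/68 the constrained rates are 0.2706 and 0.1206, so SE0 = √(0.2706 × 0.7294/136 + 0.1206 × 0.8794/68) = 0.0549, z = (−0.0147 − 0.15)/0.0549 = −3.00 and p = 0.0013. Adding abandoned attempts, all as events:

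| Added | Balloon | Control | One-sided p |
|---|---|---|---|
| 0 | 26/136 | 14/68 | 0.0013 |
| 1 | 27/137 | 14/68 | 0.0020 |
| 2 | 28/138 | 14/68 | 0.0028 |
| 9 | 35/145 | 14/68 | 0.0218 |
| 10 | 36/146 | 14/68 | 0.0274 |

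   Ten added events are needed to lose the result. Exact power of an analysis that forces the added subjects to be events is 83.6% for one and 80.6% for two. If they instead have the planned 19% event probability, it is 86.3% for either number.

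5. **Effect on a rare-event row.** Protocol 2.3.4.4.2 relies on the balloon arm to show uncommon events. Using 1 − (1 − p)^136, prevalences of 1.8%, 1.5% and 1.0% give 91.5%, 87.2% and 74.5%, which match the stated 91%, 87% and 75%. Now assume that one of the 148 randomised balloon subjects is an abandoned attempt with the only perforation. The PP row shows 0/147, with exact 95% upper limit 1 − 0.025^(1/147) = 2.5%. With him included it is 1/148 = 0.7%, exact 95% CI 0.02% to 3.7%. With two such subjects it would be 0/146 against 2/148 = 1.4%.

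**The case against.** The case against is substantial.

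- **The primary endpoint is already protected.** Protocol 2.3.4.2 specifies an ITT analysis with non-PP balloon subjects counted as failures, and 2.2.3 and 2.3.2 say the same. SAP 10.3.4.1.3 adds an ITT tipping-point analysis from all failures to all successes. A reader might infer that the one-sided exclusion threatens the non-inferiority conclusion. The documents do not support that at zero to two subjects, and another primary safety test would add little.
- **The event would not vanish.** The AE and serious-AE listings are on ITT. Table 14.2.2.4 (primary safety endpoint) and Table 14.1.4.2 (procedure information, which should carry rectal-exam problems) are also ITT. Review by the Clinical Expert and the CEC, and reporting of unanticipated device effects, are not limited to PP. It would be too strong to say that such an event appears nowhere. It is missing from the general AE summary tables.
- **The restriction rests on titles.** The table list is loosely edited and the shells are in a separate document. Still, 18 consistent labels, beside other tables that do have ITT versions, are what a programmer would follow.
- **The numbers are small and partly assumed.** The perforation is hypothetical and the two intervals overlap widely. That abandoned attempts carry more events than completed ones is plausible, but nothing in the documents shows it.

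What remains is the missing safety population and the follow-up waiver. Listings give no rate and cannot show what was not collected.

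**Conclusion.** The point holds as a gap in AE reporting and collection. Followed as written, the plan leaves a procedure-exposed balloon subject out of all 18 general AE tables and does not require his later events to be recorded. The expected number is zero to two.

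For the primary safety decision the effect is negligible at the planned rates (p = 0.0028 with two added failures). For a rare procedural harm, one omitted case is the difference between none and one in the row. That illustration assumes the case occurs in an abandoned attempt and that no implanted subject has the same event. Subjects withdrawn before any attempt raise no such concern. This is an inexpensive improvement and does not undermine the primary analysis.

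**What to change.** - In SAP section 9, define a safety population: all randomised subjects in whom the marking/implantation session was started, analysed as randomised. Name it in 10.3.6.1 and use it for Tables 14.3.1.1 to 14.3.3.2.
- Amend Protocol 2.3.2 so that AEs in abandoned attempts are collected to Month 6.
- Keep PP for the primary test and for dosimetry. No new primary safety test is needed: carry the Protocol 2.3.4.2 analysis (ITT, non-PP balloon subjects as failures) explicitly into SAP 10.3.4.1.3.
- Reconcile the PP label of Table 14.2.2.2 with the ITT wording of SAP 10.3.4.1.3 and Figure 14.2.5.

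The cost is one population definition, 18 retitled tables, a short protocol amendment and AE follow-up of zero to two subjects. The reported balloon AE rate may rise slightly. The success criterion does not change.

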# **10** Statistical Methods

## **10.1 General Statistical Considerations**

Study data will be made available in listings or electronic files, and study data will be listed by subject with the randomized treatment indicated. The study results will be summarized using descriptive statistics by randomized treatment. Summaries of baseline information will also include a total column. Standard numeric descriptive statistics include the n (observed values), mean (including the 95% confidence interval), standard deviation, median, minimum, and maximum values. Categorical data will be summarized with counts and percentages calculated based on non-missing values. Measures summarized across multiple visits will be summarized by visit, and a change from baseline will be provided for numeric variables.

A two-sided p-value of less than or equal to 0.05 or a one-sided p-value of less than or equal to 0.025 will be considered statistically significant unless otherwise specified.

All statistical analyses and summaries will be generated using SAS version 9.4.

<sup>1 HHS, FDA (1998). Guidance for industry: E9 Statistical Principles for Clinical Trials

<sup>2 SAS software. Version 9.4. Copyright © 2016 SAS Institute Inc., Cary, NC, USA.

Statistical Analysis Dlan	Client/Project	BioProtect BP-007
Statistical Allalysis Flan	Version and Date	V2 05-DEC-2021

#### **Handling of Missing Data**

The handling of missing data from the primary safety and efficacy analyses is addressed through the sensitivity analyses identified in Sections 10.3.4.1.3 and 10.3.4.2.3. All other summaries will be based on available data, without imputation of missing data.

### **10.2** Adjustments for Multiplicity of Endpoints

The study has two co-primary endpoints. Each co-primary endpoint will be tested using one-sided alpha equal to 0.025 tests. To control the overall type I error, both co-primary hypotheses must be met to declare success on the primary analysis.

If both co-primary endpoints reach success for the study, then the following three secondary analyses will be performed for consideration in labeling by testing for the superiority of ProSpace to the control:

- The primary safety endpoint will be evaluated using a two-sided Fisher's Exact test in order to assess superiority of ProSpace safety.
- The secondary endpoint rate of Grade 2 or greater rectal adverse events that are also devicerelated, marking/implantation procedure-related, or IMRT-related with a duration of at least 5 days will be evaluated using a two-sided Fisher's Exact test.

The additional endpoints will be evaluated using two-sided tests. The secondary analyses will control for multiplicity to maintain an overall Type I error rate of 0.05. If any of these should reach significance at the 0.0167 level, then the results would be considered supportive of an additional claim or claims (i.e., a Bonferroni will be used to control for multiplicity).

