# 6 Sample Size Justification

The sample size of 222 (74 in the *Control Group* and 148 in the *ProSpace Group*) was derived to achieve at least 80% power to meet the study co-primary endpoints (safety and efficacy) and to allow for an 8% drop-out rate at 6 months where the primary endpoints are evaluated. A sample of 204 evaluable subjects (68 in the *Control Group* and 136 in the *ProSpace Group*) will provide at least 80% overall power to meet both study co-primary analyses.

For sample size estimation we assume that the co-primary safety and efficacy endpoints are independent. Should positive dependency exist the actual power will be somewhat larger than the calculation presented in this section. Thus, the presented power estimation can be viewed as a lower bound of the actual study power.

For the primary safety endpoint, assuming that the rate of AEs is 21% and 19% in the *Control* and *ProSpace Groups*, respectively, the proposed sample size yields power of 85% to succeed on the primary safety analysis. The power was estimated using Farrington-Manning test with a non-inferiority margin of 15.0% and one-sided alpha of 0.025. Additionally, the events used for the safety analysis will have been adjudicated by a CEC and the outcome of that adjudication will be used for the purpose of this analysis.

Statistical Analysis Plan	Client/Project	BioProtect BP-007
	Version and Date	V2 05-DEC-2021

For the primary efficacy endpoint, assuming the true response rate in the *ProSpace Group* is 87.5%, the sample of 136 evaluable subjects will provide at least 95% power to succeed on the primary effectiveness analysis based on a one-sided 0.025 exact binomial test.

Assuming that the two co-primary endpoints are independent, the overall study power is at least 80% (0.85 for the safety endpoint and  $\sim$ 0.95 for the efficacy endpoint).

The proposed sample size is also sufficient to capture rare / uncommon adverse events. For example, the proposed sample size for the ProSpace arm provides 91% chance of observing at least one AE whose prevalence in the intended use population is 1.8% 87% chance of observing at least one AE whose prevalence in the intended use population is 1.5%; and 75% chance of observing at least one AE whose prevalence in the intended use population is 1.0%.

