#### 10.3.4.1 Co-Primary Safety Endpoint and Analysis

#### 10.3.4.1.1 Primary Safety Endpoint

The adverse events qualifying as primary safety events will be determined through adjudication by the CEC. The primary safety endpoint is based on the occurrence of one or more adverse event as follows, as indicated on the CEC CRF:

- Event is indicated to be a Grade 1 or greater rectal event lasting at least 2 days through the first 183 days (6 months) and
- Event meets one of the relatedness classifications:
  - Event is indicated to possible, probably, or definitely device-related;
  - Event is related to marking or
  - Event is related to the balloon implantation procedure.

Note that events related to anesthesia or to the use of a foley catheter will not be considered marking or implantation procedure-related.

Subjects will be counted as having an event if one occurs anytime through Day 183 (6 months) from the marking date or as not having an event if they record no events and are followed through at least Day 169 (6 month minus 14 days) from the marking date. Subjects who terminate the study before Day 169 and did not experience the AE of interest will be considered missing from the PP population and not included in the primary safety analysis. The impact of these subjects will be evaluated in a sensitivity analysis for the primary safety endpoint as described below.

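### The SAP's first labelling superiority test uses an endpoint that does not count rectal events due to IMRT alone, so it cannot plausibly show the benefit the balloon is meant to bring

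*SAP*

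**What the plan says.** - **The labelling tests (SAP 10.2).** If both co-primaries succeed, "the following three secondary analyses will be performed for consideration in labeling". The first reads: "The primary safety endpoint will be evaluated using a two-sided Fisher's Exact test in order to assess superiority of ProSpace safety". The section intends to "maintain an overall Type I error rate of 0.05", and a claim is supported "If any of these should reach significance at the 0.0167 level". Three analyses are announced, but only two bullets follow.
- **The endpoint (SAP 10.3.4.1.1).** The event must be a "Grade 1 or greater rectal event lasting at least 2 days through the first 183 days (6 months) and" it must also satisfy a second condition: "Event meets one of the relatedness classifications". The classes are device-related, marking-related and related to the balloon implantation. IMRT is not among them. SAP 3.1 and SAP 5 define the endpoint in the same way.
- **The second labelling test (SAP 10.2).** The Grade 2 bullet does name IMRT as a cause: "marking/implantation procedure-related, or IMRT-related with a duration of at least 5 days".
- **The protocol.** Sections 2.2.2.3 and 2.3.4.1 count rectal events of Grade 1 or above lasting at least 2 days, together with implantation-procedure events. They attach no cause filter to the rectal events. Protocol 2.3.3 runs the superiority test on that endpoint and names a third test, EPIC genitourinary toxicity on the last IMRT day.
- **Arms and rationale.** Both arms receive IMRT and marking, and the balloon is an addition (protocol 2.2.1). The protocol's benefit-risk discussion gives less rectal radiation, and hence less rectal toxicity, as the expected gain.

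**The concern.** A superiority test of balloon safety should be able to register what the balloon is expected to improve, namely rectal toxicity caused by radiation. Under the SAP definition a rectal event attributed only to IMRT is not counted in either arm. What remains is marking-related events, to which both arms are equally exposed, plus device and implantation events, which only balloon men can have. To win, the balloon would have to reduce events caused by the marking procedure, and the documents offer no mechanism for that.

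Two things are at stake. A null result would be close to certain and could be misread as evidence of no rectal benefit. The Bonferroni share reserved for this test also tightens the threshold for the other labelling claims.

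**Working it through.** **Inputs.** 136 balloon and 68 control evaluable men; planning rates 19% and 21%; margin 15 points; one-sided 0.025 (protocol 2.3.4.4, SAP 6). Labelling tests are two-sided Fisher at 0.0167 (SAP 10.2).

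**1. The plan's own figure.** Farrington-Manning power uses the null-restricted rates, 27.17% balloon and 12.17% control:
- s0 = √(0.2717×0.7283/136 + 0.1217×0.8783/68) = 0.0550
- s1 = √(0.19×0.81/136 + 0.21×0.79/68) = 0.0598
- power = Φ[(0.15 + 0.02 − 1.96×0.0550)/0.0598] = 0.851

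The stated 85% is reproduced.

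**2. Alpha share.** 0.05/3 = 0.0167 per test, so this test takes one third. Spread over two tests, each would have 0.05/2 = 0.025.

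**3. Chance of a win under the SAP definition.** Let m be the marking-related rate, common to both arms, and e ≥ 0 the added device or implantation risk. The control rate is m and the balloon rate is 1 − (1−m)(1−e). All 137 × 69 tables were enumerated, and only rejections at 0.0167 in the balloon's favour were counted. The documents give no values for m or e, so a range is shown.

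| m | e = 0 | e = 1% | e = 2% |
|---|---|---|---|
| 0.5% | 0.02% | 0.006% | 0.002% |
| 1% | 0.15% | 0.04% | 0.01% |
| 3% | 0.7% | 0.2% | 0.07% |
| 5% | 0.6% | 0.2% | 0.1% |
| 10% | 0.7% | 0.4% | 0.2% |
| 21% | 0.7% | 0.5% | 0.3% |

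The column e = 0 is the best case, and it never exceeds about 0.7%. The requirement that both co-primaries succeed first can only lower these figures. In counts: even with 0/136 balloon events, a win needs at least 4/68 control events (p = 0.0116; 3/68 gives p = 0.036), all from a marking procedure that both arms undergo.

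**4. What the reserved alpha costs elsewhere.** No Grade 2 or EPIC effect sizes are given, so every rate here is an assumption.

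| Test | Balloon vs control | Power at 0.0167 | Power at 0.025 |
|---|---|---|---|
| Grade 2, Fisher | 3% vs 10% | 30% | 40% |
| Grade 2, Fisher | 2% vs 10% | 47% | 57% |
| Grade 2, Fisher | 5% vs 15% | 46% | 52% |
| Grade 2, Fisher | 8% vs 20% | 48% | 54% |
| Grade 2, Fisher | 5% vs 20% | 78% | 82% |
| EPIC, normal approximation | 0.4 SD | 62% | 67% |

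The cost is roughly 3 to 10 points per test. It presumes that the third test is the EPIC comparison, which only protocol 2.3.3 names.

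**5. What adding IMRT-related events would do.** At 19% versus 21% the favourable power is 1.8% whichever causes are counted. Against an assumed 21% control rate it is about 36%, 55% and 83% if the balloon rate were 10%, 8% and 5%. A gap of that kind is possible once radiation events count; the SAP definition offers no route to it.

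**The case against.** - **Limited consequence.** The test runs only after both co-primaries succeed, concerns an optional claim, and does not inflate type I error. Testing superiority on the same endpoint after non-inferiority is a coherent, pre-specified step, and spending alpha on a long shot is the sponsor's choice. All of this stands. It limits the weight of the point but does not make the test informative.
- **The root lies elsewhere.** The bullet largely repeats the protocol's test. It fails only because the SAP narrowed the endpoint beneath it, and SAP 3.2 does not discuss what that does to superiority. This is fair: restoring the protocol endpoint would remove the problem. The narrower fix is offered because it leaves the co-primary alone.
- **Low power at the planning rates.** A reader might take the 1.8% at 19% versus 21% as the effect of leaving out IMRT events. It is not: it follows from a two-point difference in 204 men and would remain after the fix.
- **Contradictory bullets.** A reader might infer that the two SAP 10.2 bullets contradict each other because only one names IMRT. They define different endpoints, so different cause lists are not in themselves an error. The real conflict is between the Grade 2 bullet and SAP 10.3.5.1, which joins the rectal criterion and the relatedness list with *or* and has no IMRT class.
- **All IMRT events excluded.** A reader might infer this too. The SAP expressly excludes only anaesthesia and Foley catheter events, and an IMRT-related event also judged device- or marking-related still counts. The device route, however, can add events only to the balloon arm.

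**Conclusion.** The concern holds in this limited form. As defined in the SAP, the first labelling test cannot plausibly show reduced radiation-induced rectal toxicity. Its chance of favouring the balloon is at most about 0.7% for equal arm rates between 0.5% and 21%, and lower with any added device or implantation risk. This rests on reading the relatedness list as exhaustive and on equal marking risk in the two arms.

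The loss to the other labelling tests, roughly 3 to 10 points, rests on assumed effect sizes and on a three-test family that the SAP announces but does not fully list. The documents do not support the stronger conclusion that either co-primary result, or control of type I error, is compromised.

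**What to change.** Before unblinding, amend SAP 10.2:

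1. For the superiority test only, count CEC-adjudicated rectal events of Grade 1 or above, lasting at least 2 days, through Day 183, that are related to the device, the marking or implantation, or IMRT. Counting rectal events of any cause, as in the protocol, would also serve. Leave the non-inferiority co-primary unchanged.
2. State that this makes a benefit detectable but does not by itself give adequate power, and show the figures in step 5 with their assumed rates. If the sponsor prefers not to redefine the test, the alternative is to drop it and divide 0.05 over the remaining tests.
3. Reconcile the three announced analyses with the two listed, stating whether the EPIC test in protocol 2.3.3 is the third.
4. Reconcile the Grade 2 definition in SAP 10.3.5.1 with the second bullet of SAP 10.2, on both the connective and the IMRT class.

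The cost is SAP wording and the matching table shells. SAP 10.3.6.1 already provides for CEC adjudication of IMRT-relatedness and rectum-relatedness, so no new data collection is foreseen.
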